## Supplement 6. FMT Long-term Adverse Outcomes (up to 2 years by physician report and 10 years by patient report)

- Characteristics
  - Height
  - Weight
- Serious Infection (HIV, viral hepatitis, prion, etc)
  - *Use of new drugs* 
    - o Describe
  - Surgeries or other Procedures
    - Describe
- Diagnosis of any new condition
  - o Autoimmune (hypothyroid, ITP, RA, SLE, MS, celiac, Type I diabetes, Sjogrens)
  - o Asthma
  - Allergy/atopy
  - Metabolic disease
    - Diabetes II
    - Obesity
  - o Psychiatric disorder
  - Neurologic disease
    - Parkinson's disease
    - Amyotrophic lateral sclerosis (ALS)
    - Autism spectrum diagnosis
  - Cardiovascular disease
    - Myocardial infarction
    - Coronary artery revascularization
    - Cerebrovascular accident
    - Hypertension
  - o Colon cancer
  - Other malignancy
  - Inflammatory bowel disease
    - Crohn's
    - Ulcerative colitis
    - IBD-U
  - o IBS
- IBS-C
- IBS-D
- IBS-M
- o Other
- Hospitalization
  - o Reason for hospitalization
  - o FMT related (related, possibly related, unrelated)
- Life-threatening illness
  - o Describe/diagnosis
  - o FMT related (related, possibly related, unrelated)
- Death
  - Cause of death
  - o FMT related (related, possibly related, unrelated)

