#### 4.4.2 Data Collection and Follow-up of Withdrawn Participants

When participants notify study staff that they no longer wish to participate, study staff will request final-visit information from the participant and their healthcare provider. If the participant informs the study staff that they wish to withdraw consent, no further data will be sought from them or their healthcare provider. Data that was previously collected when the patient was actively enrolled will be retained in the registry.

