#### **5.1** Data Elements

Data elements that may be collected for the FMT registry are shown in Supplements 1-6. In order to make the data elements as broad and inclusive as possible, the FMT Registry Steering Committee developed the data elements based on current guidelines and published recommendations, their own treatment protocols/experience, and feedback from 15 additional large FMT practice sites. *Supplement 1* details the data elements related to FMT technique including donor and recipient screening. For sites that employ a donor questionnaire, *Supplement 2* provides potential questions used on a questionnaire, based on those used for blood transfusion. *Supplement 3* shows the data elements for baseline characteristics of donors and recipients and for FMT treatment indications, while *Supplement 4* provides effectiveness outcomes data elements. Finally, *Supplements 5* and 6 detail data elements for short-term and long-term safety outcomes. Patients will be followed at regular intervals for up to 10 years after FMT for pre-defined and spontaneously reported adverse events and for pre-defined outcomes of effectiveness. Investigators will enter follow-up data at 1 month, 6 months, 1 year and 2 years post-FMT, and patients will then provide data annually up to 10 years.

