#### 6.1 Adverse Events

Based on numerous case reports and small clinical studies in the literature, it appears that FMT for refractory CDI is generally well-tolerated and safe, although occasional adverse events (e.g., febrile

episodes) have been reported. Importantly, a prospective systematic evaluation of both immediate and short-term predefined adverse outcomes in a large number of patients undergoing FMT is currently lacking. In the absence of any consensus guideline on practice standards for FMT in the U.S. and the lack of regulatory oversight for the treatment of refractory CDI, the committee has learned through polling of sites performing FMT that there is a wide variation in the practice of FMT. This variance in practice also raises potential concerns about risks for both short-term and long-term risks. As discussed in section 5.1, to broadly capture adverse outcomes in recipients of FMT that may be indicative of a safety concern, we have developed two data entry fields: 1) Short-Term Adverse Outcomes (within 30 days)—Supplement 5, and 2) Long-term Adverse Outcomes (up to 2 years reported by the physician and 10 years reported by the patient)—Supplement 6. Adverse event information will be provided by the FMT provider site at four time points post-FMT: 1 month, 6 months, 1 year, and 2 years. In addition, patients will be contacted directly by email and text at least annually for up to 10 years to provide follow-up information via a dedicated portal maintained by the Icahn School of Medicine at Mt. Sinai.

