## 6.2 Classification of Events

#### 6.2.1 Relatedness

The site Investigator will assess the relationship of SAEs to FMT, as related or not related, based on clinical judgment and using all available information, and may include consideration of the following factors:

- Possible alternative causes of the SAE, including the disease under treatment, pre-existing
  conditions, concomitant use of other drugs, and presence of environmental or genetic
  factors.
- The temporal association between FMT exposure and onset of the SAE.
- Whether the manifestations of the SAE are consistent with known actions or theoretical toxicity of FMT.

The causal relationship between FMT and the SAE will be assessed using one of the following categories.

- 1. Not Related:
  - Temporal relationship is lacking (e.g., the event occurred before FMT); or
  - Other causative factors explain the event (e.g. pre-existing condition, other concomitant treatment);
- 2. Possibly Related:
  - Positive temporal relationship (e.g., the event occurred within a reasonable time frame following FMT); and
  - The SAE is possibly explained by FMT and/or, and there is a lack of other causal factors.
- 3. Related:
  - Positive temporal relationship (e.g., the event occurred within a reasonable time frame following FMT); and
  - The SAE is more likely explained by FMT than by other causes.

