## 6.3 Serious Adverse Events (SAE)

The only type of adverse event that may occur related to participation in the FMT registry is breach of privacy/confidentiality.

Clinical SAEs that are recorded in the registry will have the standard definition, which includes the following:

- Death
- Life-threatening (patient was at substantial risk of dying)
- Hospitalization (initial or prolonged)
- Disability or permanent damage
- Congenital anomaly/birth defect
- Other important event (may jeopardize patient and may require to prevent one of other outcomes)

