## 6.4 Reporting Procedures

All spontaneous and pre-specified AEs reported by participants or healthcare providers will be recorded in the Registry database. Predefined short-term and long-term AEs are presented in *Supplements 5* and 6. Analyses of all AEs (including spontaneous and pre-defined AEs and SAEs) will be provided to the Registry Steering Committee and the OSMB at least twice yearly for their review. Summaries of AEs (including spontaneous and pre-defined AEs and SAEs) will be submitted to IRB and NIH during the annual review of the registry.

Breach of privacy and suspected unexpected SAEs will be reported to the Registry Steering Committee Chair and Co-Chair and the OSMB within 5 days of identification of the event. These events will also be reported to the local site IRB per local reporting criteria.

All participants are given a toll-free number to contact the Investigators directly if they have any safety issues or concerns.

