For follow-up beyond 2 years, the ePRO system allows the registry staff to automatically contact the patient for follow-up information. For example, patients can receive an automatic text message or email that opens to a follow-up electronic questionnaire for long-term follow-up. The link to the ePRO also will be embedded in the patient education app that will include content (videos and written information) approved by the steering committee related to FMT indications, preprocedure checklist, potential adverse events, and post-procedure follow-up. The app will be maintained at Sinai AppLab, Icahn School of Medicine at Mount Sinai and will be made available to all FMT patients enrolled in the registry.

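### Death is on the list of outcomes collected to 10 years, but after year 2 the only scheduled informant is the patient, so late mortality will be under-counted

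*Protocol*

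**What the plan says.** Supplement 6 is a single list under a single title, "FMT Long-term Adverse Outcomes (up to 2 years by physician report and 10 years by patient report". Death, with its cause and its relation to FMT, is one of the items. The title gives two reporters and two horizons but does not assign individual items to either reporter.

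The follow-up schedule is in three places. Section 5.1: "Investigators will enter follow-up data at 1 month, 6 months, 1 year and 2 years post-FMT, and patients will then provide data annually"; the patient's part runs until year 10. Section 6.1: "Adverse event information will be provided by the FMT provider site at four time points post-FMT", the last of which is 2 years, with patients contacted directly by email and text at least annually to 10 years. Section 3.1 gives the same provider time points and the same 10-year patient contact. Section 9.1 describes the later mechanism: "For follow-up beyond 2 years, the ePRO system allows the registry staff to automatically contact the patient for follow-up information".

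Two other routes could carry news of a death. Section 6.4: "All spontaneous and pre-specified AEs reported by participants or healthcare providers will be recorded in the Registry database". Section 4.4.2: once a participant has said that they wish to stop, "study staff will request final-visit information from the participant and their healthcare provider"; if consent is withdrawn, nothing further is sought.

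**The concern.** A patient who has died cannot complete the form. After year 2 the protocol schedules no other informant: the visible text has no proxy or next-of-kin report, no linkage to death records, no provider contact and no vital-status check when a patient stops responding.

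Long-term safety is part of the primary objective (Section 2.1), and Section 2.2.1 names long-term events as the greater concern. Section 8.3 bases the registry's advantage over spontaneous reporting on complete numerators. For deaths after year 2 the registry would itself depend on spontaneous reports. The error runs one way: missed deaths make late mortality look lower than it is, which in a safety registry is false reassurance.

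**Working it through.** The protocol gives no figure to reproduce here. The check has three parts.

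**1. Who can report a death after year 2**

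| Route | Where | Scheduled or triggered after year 2? |
|---|---|---|
| Provider entry | 3.1, 5.1, 6.1 | No; the last entry is at 2 years |
| Patient form by email or text | 5.1, 6.1, 9.1 | Yes, but not by a patient who has died |
| Unprompted report by participant or provider | 6.4 | Recorded if made; nothing prompts it |
| Final provider information | 4.4.2 | Only after the participant gives notice |

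No row prompts a report of a death in years 2 to 10.

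**2. How many deaths would fall in that period (scale only)**

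Inputs: N = 4,000 (Section 8.1). Annual death probability q is assumed flat at 0.5% to 3%. The range includes 1.75%, which Section 8.3 gives for age 68, the median age of the claims cohort and not of the registry. No dropout is assumed.

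- Deaths by year 2 = N[1 − (1 − q)²]
- Deaths by year 10 = N[1 − (1 − q)¹⁰]
- Deaths after year 2 = N[(1 − q)² − (1 − q)¹⁰]

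At q = 1.75%: (0.9825)² = 0.9653 and (0.9825)¹⁰ = 0.8382, giving 138.8 deaths by year 2, 647.4 by year 10 and 508.6 between.

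| q per year | By year 2 | By year 10 | After year 2 | Share after year 2 |
|---|---|---|---|---|
| 0.5% | 39.9 | 195.6 | 155.7 | 79.6% |
| 1% | 79.6 | 382.5 | 302.9 | 79.2% |
| 1.75% | 138.8 | 647.4 | 508.6 | 78.6% |
| 3% | 236.4 | 1,050.3 | 813.9 | 77.5% |

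The share is close to 8 years out of 10, as flat mortality implies. If q instead starts at 1.75% and rises by an assumed 8% a year, 762.1 of 906.4 deaths (84.1%) fall after year 2.

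**3. Whether censoring at last contact repairs the rate**

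Let λ = −ln(1 − q). True person-years in years 2 to 10 are the deaths in that period divided by λ. Suppose that no later death is reported and each such patient is censored at the last annual form before death, losing about half a year.

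- q = 1.75%: λ = 0.01765; 508.6 / 0.01765 ≈ 28,808 person-years; loss about 508.6 × 0.5 ≈ 254, leaving 28,554 (99.1%).
- q = 0.5%: 31,054 falls to 30,976 (99.75%).
- q = 3%: 26,721 falls to 26,316 (98.5%).

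Nearly all the denominator remains while the deaths are lost. If a fraction f of late deaths reaches the registry, the observed rate is therefore about f times the true rate. At q = 1.75% and f = 0.5 it is 0.887 against 1.765 per 100 person-years, a ratio of 0.502. The documents give no basis for a value of f.

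**The case against.** The strongest reply is that Supplement 6 is a menu. Section 5.1 describes the supplements as elements that may be collected, and a pooled list under two reporters can be read as leaving physicians to supply, up to 2 years, what only they can supply. That reading is fair. It still leaves years 2 to 10 with no scheduled source for death, and Supplement 6 does not say that death stops at year 2. Either reading needs a correction to the text.

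The consent pages are not shown and may already collect a proxy contact or permission for record linkage. This stands, and the fix is conditional on it. It also stands that the shares above rest on assumed mortality and no dropout, and that the quantity which sets the bias, f, is unknown.

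Four stronger readings are tempting and are not supported:

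- A reader might infer that nobody could report a late death. Section 6.4 records any provider report that is made; the gap is that none is prompted.
- A reader might infer that the relatedness of a late death has no assessor. Section 6.2.1 says "The site Investigator will assess the relationship of SAEs to FMT, as related or not related", with no time limit, and Section 6.3 counts death as an SAE. The duty follows from the event, so a death that reaches the registry is covered. The gap is in detection.
- A reader might infer that missed deaths are beyond recovery. Section 9.1 has direct identifiers kept apart from outcome data with linking codes. A later vital-status check is not planned in the visible text, but it is not ruled out.
- A reader might extend the point to all long-term safety. Surviving patients can report new diagnoses, hospitalisations and life-threatening illness.

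**Conclusion.** The point holds for detection of deaths after year 2. Followed as written, the protocol lets most late deaths appear as non-response, and observed mortality in years 2 to 10 is biased downward by a factor of about f, which is unknown. Under flat mortality of 0.5% to 3% a year and no dropout (both assumed), about 78% to 80% of 10-year deaths, or 156 to 814 of 4,000 patients, fall in that period. These counts show how many deaths are exposed to the gap, not how many would be missed.

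The survival comparison in Section 8.3 is not affected, since its mean follow-up of 1.70 years lies within the window of provider entries. The protocol should be corrected, because the gap is in what is collected and bears on the primary objective.

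**What to change.** Amend Sections 5.1 and 6.1 and Supplement 6 together.

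1. Record a proxy contact at enrolment, unless the consent pages already do so, who may complete the annual form or report a death.
2. Where feasible, when an annual form after year 2 goes unanswered, send the enrolling site a brief vital-status query: alive, dead (with date and cause), or unknown. Exclude participants who withdrew consent, as Section 4.4.2 requires. Any death found is then assessed under the existing Section 6.2.1.
3. If neither is feasible, mark death in Supplement 6 as physician report to 2 years and limit mortality reporting to that window.

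The cost is one contact field plus site work after the last scheduled entry. That work is not trivial: 4,000 patients × 8 annual forms is at most 32,000 forms, so an assumed 20% to 50% non-response would mean about 6,400 to 16,000 queries. Over 75 sites and 8 years this is roughly 11 to 27 per site per year (6,400 / 600 and 16,000 / 600). If that is too much, the proxy contact alone is the cheaper step. The fallback in item 3 costs only a text change but gives up mortality after year 2.

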## Supplement 5. FMT Short-term Adverse Outcomes (within 30 days)

- Procedure-related
  - Sedation complication
  - Bleeding
  - Perforation
  - o Other
- Symptoms post-FMT (within 30 days)
  - Diarrhea
  - Constipation
  - Nausea and/or vomiting
  - o Bloating
  - Abdominal pain
  - o Fever
  - Headache
  - Rash
  - Weight gain or loss
  - Other\_\_\_
- Surgeries or other Procedures
  - Describe
- Documented Infection (any)
  - Specify site/organism
  - o FMT related (related, possibly related, unrelated)
- Hospitalization
  - o Reason for hospitalization
  - o FMT related (related, possibly related, unrelated)
- Life-threatening experience
  - Describe/diagnosis
  - o FMT related (related, possibly related, unrelated)
- Death
  - Cause of death
  - o FMT related (related, possibly related, unrelated)
  - o Site of death
    - Hospital
    - Home
    - Convalescent or skilled nursing facility

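### Supplements 5 and 6 have items for only three of the six SAE criteria in 6.3, and Supplement 6 has no relatedness field for serious infection or new diagnoses

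*Protocol*

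**What the plan says.** Protocol 6.3 states: "Clinical SAEs that are recorded in the registry will have the standard definition, which includes the following". Six criteria follow: death; "Life-threatening (patient was at substantial risk of dying"; "Hospitalization (initial or prolonged"; "Disability or permanent damage"; "Congenital anomaly/birth defect"; and a residual class of other important events.

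Protocol 6.2.1 sets the assessment duty: "The site Investigator will assess the relationship of SAEs to FMT". It names the time between FMT and onset as one factor and gives three categories (not related, possibly related, related). Under 6.2.2, SAEs judged related or possibly related are then classed as expected or unexpected. Under 6.4, suspected unexpected SAEs go to the Steering Committee chairs and the Observational Study Monitoring Board (OSMB) within 5 days. All adverse events (AEs) are recorded and analysed for both bodies at least twice a year.

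Protocol 6.1 describes Supplement 5 (within 30 days) and Supplement 6 (to 2 years by physician, to 10 years by patient) as the two data entry fields developed to capture adverse outcomes. Supplement 5 has "Documented Infection (any" with a relatedness line. Supplement 6 has "Serious Infection (HIV, viral hepatitis, prion, etc" and a list of new diagnoses, both without one.

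**The concern.** Short-term and long-term safety is the primary objective (2.1). Section 2.2.1 gives the greater weight to late harm: serious conditions arising from transferred microbiota, including infection and chronic disease. Supplement 6 is where such harm is recorded, yet it carries fewer prompts for SAE assessment than the 30-day form. Relatedness is asked for any infection in the first month, but not for one labelled serious that is found later.

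Take a malignancy or amyotrophic lateral sclerosis (ALS) diagnosed in an outpatient and entered at the 6-month, 1-year or 2-year site report. It may meet the disability or other-important-event criterion of 6.3, and neither condition is on the list of known events in 6.2.2. If it is serious and suspected to be related, 6.4 puts it on the 5-day route. Nothing in the listed item prompts the site to ask whether it is serious, when it began or whether it is related. At stake is how completely and uniformly 75 sites identify late SAEs. Details not collected at follow-up may not be recoverable later.

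**Working it through.** No sample-size, power or error-rate calculation bears on this point. The check sets the definition in 6.3 against the listed items.

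**Step 1. Seriousness criteria against items**

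| Criterion in 6.3 | Supplement 5 | Supplement 6 |
|---|---|---|
| Death | item, with relatedness | item, with relatedness |
| Life-threatening | item, with relatedness | item, with relatedness |
| Hospitalization | item, with relatedness | item, with relatedness |
| Disability or permanent damage | none | none |
| Congenital anomaly | none | none |
| Other important event | none | none |

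Three of six criteria have an item; 6 − 3 = 3 do not. Supplements 3 to 6 contain no pregnancy or pregnancy-outcome item. Pregnancy appears in Supplement 1 only, as a possible site exclusion.

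**Step 2. Relatedness lines**

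- Supplement 5 has four: documented infection, hospitalization, life-threatening experience, death. Its procedure-related items (sedation complication, bleeding, perforation, other) have none.
- Supplement 6 has three: hospitalization, life-threatening illness, death. The line on infection is gone.
- New-condition classes in Supplement 6 without a relatedness line: autoimmune, asthma, allergy/atopy, metabolic, psychiatric, neurologic, cardiovascular, colon cancer, other malignancy, inflammatory bowel disease and irritable bowel syndrome. That is 11, or 12 if the closing entry for other conditions is read as its own class.

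**Step 3. Timing**

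Supplement 6 lists no onset date. Site reports fall at 1, 6, 12 and 24 months, so the gaps are 6 − 1 = 5, 12 − 6 = 6 and 24 − 12 = 12 months. On the listed elements alone, an event is placed only within such a gap, while 6.2.1 asks the investigator to weigh its temporal association with FMT. Supplement 5 lists no onset date either, but its 30-day window bounds the uncertainty.

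**Step 4. Who reports**

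After 2 years the data come from patients alone (5.1, Supplement 6), whereas 6.2.1 gives the relatedness judgement to the site investigator. No route from the patient's report to the site is described.

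**Step 5. Expectedness of infections**

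The list of known events in 6.2.2 includes bacterial, viral, fungal and parasitic infection, and events determined to be expected go into an annual summary. A late HIV or viral hepatitis infection could be classed as expected whatever the form records. Form fields and the rules in 6.2.2 to 6.4 therefore have to be considered together.

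**The case against.** The strongest reply has four parts.

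*The supplements are not the final form.* Section 5.1 describes them as elements the registry may collect, and the electronic case report form is not shown; it may hold a general SAE page. This stands as a limit on the point. But 6.1 presents Supplements 5 and 6 as the entry fields, 6.4 treats them as the predefined events, and no SAE page is mentioned.

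*The duties are general.* A reader might infer that late serious infections and new diagnoses bypass SAE assessment. The Protocol does not support that. Section 6.2.1 covers SAEs whichever item they come from, and 6.4 has all spontaneous and predefined AEs recorded and reviewed at least twice a year. Staff must also pass training on reporting unexpected events (3.2). What remains is that three criteria rest on unprompted recognition. Section 8.3 itself argues for predefined outcomes over spontaneous reporting because the latter has incomplete numerators.

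*Many events are still caught.* Any infection or diagnosis leading to hospitalization, a life-threatening illness or death also enters through an item with relatedness, and the infection label already says serious. This stands and narrows the gap to events without those outcomes.

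*Relatedness on every event would go too far.* Section 6.2.1 asks it of SAEs only, and patients cannot supply the investigator's judgement in years 2 to 10. Accepted; the fix is limited accordingly.

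**Conclusion.** The point holds as a mismatch between the SAE definition and the listed data elements. Three of six criteria have no item. Serious infection and all 11 or 12 new-condition classes in Supplement 6 lack a relatedness line, and Supplement 6 lists no onset date. Long-term SAEs without hospitalization, life-threatening illness or death therefore depend on the site noticing them unprompted. How many such events there will be cannot be derived from the Protocol.

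This assumes that the entry form follows Supplements 5 and 6 as listed. If it already has a general SAE page with all six criteria, relatedness and onset, what remains is to align the supplements with it.

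Two further inferences are tempting but unsupported. One is that a late HIV or hepatitis infection would wait months for a twice-yearly review solely because a field is missing; 6.2.2 lists viral infection as a known event, so the 5-day route might not apply even with the field present. The other is that a primary SAE incidence would cover only three criteria. Section 2.1 gives a general safety objective and 8.3 plans descriptive incidences; neither names SAE incidence as a primary result or restricts what counts.

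The change is cheap and should be made, because it bears on the primary objective.

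**What to change.** - **Site-reported events, to 2 years.** Add to the serious-infection, new-diagnosis and procedure-related items a seriousness check covering all six criteria of 6.3 and an onset date. Where any criterion is ticked, open the 6.2.1 relatedness categories.
- **Pregnancy outcome.** Add a follow-up item so that the congenital-anomaly criterion can be recorded.
- **Patient-reported events, years 2 to 10.** Ask seriousness and onset date only, unless the Protocol states a route by which a site obtains the report and judges relatedness.
- **Text.** Reconcile 6.2.2, 6.3, 6.4 and Supplement 6, so that it is clear how a late serious infection is classified and reported given the infections listed as known events. Form fields alone do not settle this.

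Cost: a few fields and a conditional trigger in the data-capture system, some extra data entry, more SAE assessments by sites and a higher recorded SAE count. Reports should note that a rise after the change may reflect better capture.
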